**Table 16-2: Schedule of study procedures for SP848 (Year 2)**

Study SP848	Year 2								Safety Follow-Up
	V10	TC b	V11	V12	V13/ TermV	ETV c	Unsch Visit d	Final Visit e	
Visit a	60		72	84	96				TC f
Weeks in study									
Concomitant medications	X	X	X	X	X	X	X	X	X
Concomitant AEDs	X	X	X	X	X	X	X	X	X
Physical exam (complete)					X	X		X	
Physical exam (brief)	X		X	X			X		
Neurological exam (complete)					X	X		X	
Neurological exam (brief)	X		X	X			X		
12-lead ECG g			X		X	X	X	X	
Blood pressure and pulse	X		X	X	X	X	X	X	
Body weight and height	X		X	X	X	X	X	X	
Clinical chemistry and hematology blood sample	X		X	X	X	X		X	
Endocrinology blood sample				X		X		X	

**Table 16-2: Schedule of study procedures for SP848 (Year 2)**

Study SP848	Year 2								Safety Follow-Up
	V10	TC b	V11	V12	V13/TermV	ETV c	Unsch Visit d	Final Visit e	
Visita	60		72	84	96				TC f
Weeks in study									
Blood sample for LCM PK	X h		X h	X h	X h	X i	X i		
Blood sample for concomitant AEDs						X i	X i		
Urinalysis (subjects aged 5 to 17 years)			X		X	X		X	
Pregnancy test j	X U		X U	X U	X U	X s		X s	
Tanner Stage k					X	X			
Clinical GIC			X		X	X			
Caregiver GIC			X		X	X			
Palatability and ease of use questionnaire			X		X	X			
Dispense LCM	X		X	X	X l	X l	X m		
LCM return/compliance	X		X	X	X	X	X m	X	
Dispense diary	X		X	X	X	X			
Diary assessment	X		X	X	X	X	X	X	
C-SSRS n	X		X	X	X	X	X o	X	
Achenbach CBCL			X		X	X			
Bayley-III scales			X		X	X			
BRIEF-P/BRIEF			X		X	X			
PedsQL			X		X	X			
AE reporting	X	X	X	X	X	X	X	X	X
Health care resource use	X		X	X	X	X	X	X	

AE=adverse event; AED=antiepileptic drug; C-SSRS=Columbia-Suicide Severity Rating Scale; ECG=electrocardiogram; ETV=Early Termination Visit; GIC=Global Impression of Change; LCM=lacosamide; PK=pharmacokinetics; S=serum; TC=telephone contact; TermV=Termination Visit; U=urine; Unsch=Unscheduled; V=Visit

- a A time window of  $\pm 7$  days relative to Visit 1 is applicable for all scheduled visits and telephone contacts (with the exception of the Safety Follow-Up telephone contact).
- b Telephone contacts are scheduled during the following weeks during Year 2: Weeks 66 and 78.
- c An Early Termination Visit must be completed for all subjects who prematurely discontinue from the study.
- d If an Unscheduled Visit is needed, then the assessments noted will be performed. Additional assessments can be performed at the investigator's discretion. If the LCM dose is decreased between scheduled clinic visits due to an AE, or if a LCM dose increase is required between scheduled clinic visits, the subject must return for an Unscheduled Visit. Height will not be recorded at an Unscheduled Visit.
- e Subjects who complete the study or withdraw prematurely from the study, and who discontinue use of LCM (ie, taper), should complete the Final Visit 2 weeks after the final dose of study medication.
- f This TC occurs 28-35 days after the last dose of LCM.
- g All subjects will be required to have a 12-lead ECG (2 interpretable recordings) conducted at LCM  $C_{max}$  1 week after an initial LCM dose increase to a LCM dose level that is  $\ge 8$ mg/kg/day or a new concomitant AED is introduced. This ECG can be conducted at an Unscheduled Visit, if necessary. Subjects having a LCM dose increase to  $\ge 8$ mg/kg/day will be required to arrive at the clinic prior to taking their morning dose of LCM. Subjects will be administered their morning LCM dose by study personnel at the clinic so that an ECG (2 interpretable recordings approximately 20 to 30 minutes apart prior to vital signs assessment) can be performed 30 minutes to 1 hour after the administration of LCM (ie, at LCM steady state  $C_{max}$ ).
- h Blood sample for LCM PK will be routinely collected for subjects enrolled at sites in Japan. Blood samples may be drawn at any time post-dosing with LCM.
- i Blood samples for LCM and concomitant other AEDs may be collected at an Unscheduled Visit or Early Termination Visit if the visit is related to an ongoing SAE.
- j For female subjects of childbearing potential, serum pregnancy tests will be performed at the Early Termination Visit and at the Final Visit. Urine pregnancy tests will be performed at Visits 10, 11, 12, and 13.
- k The Tanner Stage will be performed only for subjects who are pubescent at Visit 1 or who will enter puberty during the course of the study.
- l Lacosamide for taper will be dispensed only for subjects who achieve a dose of LCM  $\ge 6$ mg/kg/day (oral solution [syrup]) or  $\ge 300$ mg/day (tablet). It is recommended that the LCM dose be tapered gradually in weekly decrements of 4mg/kg/day (oral solution [syrup]) or 200mg/day (tablet). A slower taper of 2mg/kg/day (oral solution [syrup]) or 100mg/day (tablet) is permitted, if medically necessary. In case of an emergency, a faster taper is permitted after discussion with the medical monitor, whenever possible.
- m As applicable.
- n For all subjects  $\ge 6$  years of age already enrolled, the "already enrolled" version should be completed at the next clinic visit, and the "since last visit" version should be completed thereafter.
- o The C-SSRS assessment should be completed if the Unscheduled Visit is due to an AE.

*Clinical Study Protocol, Section 16.3 (Declarations and signatures of persons responsible for study) and Section 16.4 (Declaration and signature of investigator) were moved to new Section 18 (Declaration and signature of investigator) and new Section 19 (Sponsor declaration), respectively.*

This document cannot be used to support any marketing authorization application and any extensions or variations thereof.

REDACTED COPY

## 17.7 PROTOCOL AMENDMENT 7

### RATIONALE FOR THE AMENDMENT

This administrative amendment is to fix the numbering of exclusion criteria. During Protocol Amendment 6, Exclusion Criterion 16 was deleted. The remaining criteria should have been numbered 17 through 21, inclusive, to align with the CRF.

The rationale for removal of Exclusion Criterion 16 during Protocol Amendment 6 was to allow physicians to have these medications as options for treatment during the open-label study.

### MODIFICATIONS/CHANGES

- Exclusion Criteria 16 through 20, inclusive, were mistakenly misnumbered.

### REFERENCE

*Clinical Study Protocol, Section 4.3.2 (Exclusion criteria). Original text:*

- Subject is taking monoamine oxidase inhibitors-A (MAOI-A) or narcotic analgesics.
- Subject has epilepsy secondary to a progressing cerebral disease or any other progressively neurodegenerative disease, such as Rasmussen syndrome.
- Subject has a known sodium channelopathy, such as Brugada syndrome.
- Subject has  $>2x$  upper limit of normal (ULN) of any of the following: alanine aminotransferase (ALT), aspartate aminotransferase (AST), alkaline phosphatase (ALP), or  $>ULN$  total bilirubin ( $\geq 1.5 \times ULN$  total bilirubin if known Gilbert's syndrome). If subject has elevations only in total bilirubin that are  $>ULN$  and  $<1.5 \times ULN$ , fractionate bilirubin to identify possible undiagnosed Gilbert's syndrome (ie, direct bilirubin  $<35\%$ ).

For randomized subjects with a Baseline result  $>ULN$  for ALT, AST, ALP, or total bilirubin, a Baseline diagnosis and/or the cause of any clinically meaningful elevation must be understood and recorded in the electronic Case Report form (eCRF).

If subject has  $>ULN$  ALT, AST, or ALP that does not meet the exclusion limit at screening, repeat the tests, if possible, prior to dosing to ensure there is no further ongoing clinically relevant increase. In case of a clinically relevant increase, inclusion of the subject must be discussed with the Medical Monitor.

Tests that result in ALT, AST, or ALP up to 25% above the exclusion limit may be repeated once for confirmation. This includes re-screening.

**Subjects who were directly enrolled in EP0060 for iv LCM replacement therapy or to initiate LCM treatment are not permitted to enroll in the study if any of the following criteria are met:**

- Subjects have previously participated in a long-term, open-label LCM study.

Were revised as follows:

17. Subject is taking monoamine oxidase inhibitors-A (MAOI-A) or narcotic analgesics.
18. Subject has epilepsy secondary to a progressing cerebral disease or any other progressively neurodegenerative disease, such as Rasmussen syndrome.
19. Subject has a known sodium channelopathy, such as Brugada syndrome.
20. Subject has >2x upper limit of normal (ULN) of any of the following: alanine aminotransferase (ALT), aspartate aminotransferase (AST), alkaline phosphatase (ALP), or >ULN total bilirubin ( $\geq 1.5 \times$ ULN total bilirubin if known Gilbert's syndrome). If subject has elevations only in total bilirubin that are >ULN and  $< 1.5 \times$ ULN, fractionate bilirubin to identify possible undiagnosed Gilbert's syndrome (ie, direct bilirubin  $< 35\%$ ).

For randomized subjects with a Baseline result >ULN for ALT, AST, ALP, or total bilirubin, a Baseline diagnosis and/or the cause of any clinically meaningful elevation must be understood and recorded in the electronic Case Report form (eCRF).

If subject has >ULN ALT, AST, or ALP that does not meet the exclusion limit at screening, repeat the tests, if possible, prior to dosing to ensure there is no further ongoing clinically relevant increase. In case of a clinically relevant increase, inclusion of the subject must be discussed with the Medical Monitor.

Tests that result in ALT, AST, or ALP up to 25% above the exclusion limit may be repeated once for confirmation. This includes re-screening.

**Subjects who were directly enrolled in EP0060 for iv LCM replacement therapy or to initiate LCM treatment are not permitted to enroll in the study if any of the following criteria are met:**

21. Subjects have previously participated in a long-term, open-label LCM study.

## 17.8 PROTOCOL AMENDMENT 8

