4. Subject and caregiver (which may be a parent, legal guardian, or other delegated caregiver) are willing and able to comply with all study requirements, including maintaining a daily seizure diary.

*Was revised as follows:*

All subjects in SP848 must fulfill the following inclusion criteria:

1. A signed informed consent form has been obtained from the parent/legal guardian and assent has been obtained from the subject (when possible or as required according to local Institutional Review Boards [IRBs]/Independent Ethics Committees [IECs]).
4. Subject and caregiver (which may be a parent, legal guardian, or other delegated caregiver) are willing and able to comply with all study requirements, including maintaining a daily seizure diary.

Subjects who have participated in SP847 or other LCM pediatric clinical studies in epilepsy must fulfill the following inclusion criteria:

2. Subject has completed SP847 (or the subject discontinued SP847 due to a dose reduction or status epilepticus) for the treatment of uncontrolled partial-onset seizures, or subject has participated in other LCM pediatric clinical studies in epilepsy.
3. Subject is expected to benefit from participation, in the opinion of the investigator.

Subjects who enroll directly into SP848 without previous participation in a LCM clinical study must fulfill the following inclusion criteria:

5. Subject is male or female and  $\geq 4$  years to  $\leq 17$  years of age.
6. Subject has a diagnosis of epilepsy with partial-onset seizures.
  - a. The results of at least 1 prior electroencephalogram (EEG) AND 1 prior magnetic resonance imaging/computerized tomography scan should be consistent with the above diagnosis.
7. Subject has been observed to have uncontrolled partial-onset seizures after an adequate course of treatment (in the opinion of the investigator) with at least 1 AED (concurrently or sequentially).
8. Subject has been observed to have at least 2 countable seizures in the 4-week period prior to Screening.
  - a. In the case of simple partial seizures, only those with motor signs will be counted towards meeting the inclusion criteria (only partial seizures with a recognizable and countable manifestation).

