9. Subject is on a stable dosage regimen of 1 to 3 AEDs. The daily dosage regimen of concomitant AED therapy must be kept constant for a period of at least 1 week prior to Screening. Vagal nerve stimulation is not counted as medical therapy; however, VNS settings must be kept constant for a period of at least 1 week prior to Screening.
10. Subject is an acceptable candidate for venipuncture.

*Clinical Study Protocol, Section 4.3.2 (Exclusion criteria). Original text:*

Subjects are not permitted to enroll in the study if any of the following criteria are met:

1. Subject is receiving any investigational drugs or using any experimental devices in addition to LCM.
2. Subject meets the withdrawal criteria for the primary study (with the exception of subjects who discontinued due to a dose reduction or status epilepticus), or is experiencing an ongoing serious AE (SAE).
3. Subject has a lifetime history of suicide attempt (including an active attempt, interrupted attempt, or aborted attempt), or has suicidal ideation in the past 6 months as indicated by a positive response (“Yes”) to either Question 4 or Question 5 of the Columbia-Suicide Severity Rating Scale (C-SSRS) at Screening.

*Was revised as follows:*

Subjects are not permitted to enroll in the study if any of the following criteria are met:

1. Subject is receiving any investigational drugs or using any experimental devices in addition to LCM.
3. Subject has a lifetime history of suicide attempt (including an active attempt, interrupted attempt, or aborted attempt), or has suicidal ideation in the past 6 months as indicated by a positive response (“Yes”) to either Question 4 or Question 5 of the Columbia-Suicide Severity Rating Scale (C-SSRS) at Screening.

Subjects who have participated in SP847 or other LCM pediatric clinical studies in epilepsy are not permitted to enroll in the study if any of the following criteria are met:

2. Subject meets the withdrawal criteria for the primary study (with the exception of subjects who discontinued due to a dose reduction or status epilepticus), or is experiencing an ongoing serious AE (SAE).

Subjects who enroll directly into SP848 without previous participation in a LCM clinical study are not permitted to enroll in the study if any of the following criteria are met:

4. Subject has ever received LCM.

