### MODIFICATIONS/CHANGES

- The name and contact information for the Clinical Project Manager, Medical Director (Medical Therapeutics), and Safety Representative (Patient Safety) were updated. Update to Sponsor site fax number to other contacts is not detailed below.
- Serious AE reporting number was updated for Canada and was removed for Japan (falls under global number)
- Clarifications were added that SP847 is a completed study and that new subjects enrolling into SP848 either enroll directly or from other pediatric studies of LCM.
- Text added to clarify that up to 75 subjects may enroll in SP848 from EP0060.
- Background information was updated for current status of LCM clinical development program
- Exclusion Criterion 2 was revised to potentially allow subjects from EP0060 who either withdrew consent for the sole reason of route of LCM administration or who required more than 10 infusions to participate in SP848 pending discussion with and agreement from the Medical Monitor.
- Exclusion Criterion 9 was modified to update creatinine clearance exclusion to  $<30$ mL/min to align with the rest of the LCM program. The liver function requirements from Exclusion Criterion 9 were moved to a new exclusion criterion (19).
- Exclusion Criterion 16, which excluded use of vigabatrin or felbamate, was removed.
- Exclusion Criterion 17 and the list of prohibited medications were updated to exclude use of MAOI-A inhibitors and cannabidiols.

- Exclusion Criterion 20 was added such that subjects who initiated treatment in EP0060 could not enter SP848 if they had previously participated in a long-term open-label study.
- Clarification was added to withdrawal criteria for subjects transitioning to SP848 from EP0060.
- Sponsor language for monitoring of PDILI events was added to increase clarity for the sites and to align across programs .
- Clarification was added for prohibited concomitant medications.
- Routine blood samples for LCM PK analysis during Year 2 will be collected for subjects enrolled at sites in Japan. Across all sites, a blood sample for LCM PK analysis may be collected if the subject has an Unscheduled Visit due to a SAE.
- Blood samples for concomitant AED PK analysis were removed from Year 2 visits; however, a sample may be collected if the subject has an Unscheduled Visit due to a SAE.
- Updates to the CRF language were incorporated to accommodate use of an eCRF. Minor edits to change CRF to eCRF in Section 8 are not itemized below.

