Subjects who enroll from EP0060 will begin SP848 with an equivalent dose to the last dose they received in EP0060; however, the LCM dose may be further titrated/adjusted to a level to optimize tolerability and seizure control (up to a maximum level as described in [Section 4.4.1.3](#)). For those subjects who initiated adjunctive LCM treatment in EP0060, the recommended LCM dose titration approach is outlined in [Section 4.4.1.2](#).

*Clinical Study Protocol, Section 4.6 (Concomitant medication[s]/treatment[s]). Original text, through second paragraph:*

The following medications/therapies are prohibited during the course of this study:

- Monoamine oxidase inhibitors
- Narcotic analgesics

All concomitant medications and treatments must be recorded in the appropriate study documents (case report form [CRF] and source document).

*Was revised as follows:*

The following medications/therapies are prohibited during the course of this study:

- Monoamine oxidase inhibitor-A compounds
- Narcotic analgesics
- Cannabidiols not approved or indicated for epilepsy by a local health authority

All concomitant medications and treatments must be recorded in the appropriate study documents (eCRF and source document).

*Clinical Study Protocol, Section 5.3 (Visit 1[Week 0]). Original text, first, second, and fifth paragraphs:*

For subjects who complete SP847, Visit 1 for SP848 is the same as Day 2 of the second PK collection time period (which may include an overnight stay at a hospital or medical facility) in SP847 (Day 28 for Cohorts 1, 2, 3, and 5 with maximum recommended dose of 8mg/kg/day; Day 35 for Cohorts 2 to 5 with maximum recommended dose of 10mg/kg/day; and Day 42 for Cohorts 2 to 5 with maximum recommended dose of 12mg/kg/day). For subjects who discontinue SP847 due to a dose reduction or status epilepticus, Visit 1 is the Early Termination Visit in SP847. For subjects in SP847 who are titrated up to the maximum permitted dose of 600mg/day sooner than the study schedule would ordinarily indicate (based on body weight) and who enroll in SP848, the Early Termination Visit of SP847 will also serve as Visit 1 for SP848.

For subjects who enroll in SP848 after participation in other LCM pediatric clinical studies in epilepsy, SP848 Visit 1 will be specified in the respective primary study protocol.

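### Section 4.6 prohibits cannabidiols not approved or indicated for epilepsy, but Exclusion Criterion 17 leaves them out, so entry rule and prohibited list do not match for direct enrollers

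*Protocol*

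**What the plan says.** Three places in the protocol bear on this.

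- **Section 4.3.2, Exclusion Criterion 17**, as revised in Amendment 6 and reissued in Amendment 7: "Subject is taking monoamine oxidase inhibitors-A (MAOI-A) or narcotic analgesics". It belongs to the block for children without previous participation in an LCM study, introduced by "Subjects who enroll directly into SP848 without previous participation in a LCM clinical study are not permitted to enroll in the study" and followed by the list of disqualifying conditions.
- **Section 4.6, Concomitant medication(s)/treatment(s)**, as revised in Amendment 6: "The following medications/therapies are prohibited during the course of this study". The list that follows names MAOI-A compounds, narcotic analgesics and "Cannabidiols not approved or indicated for epilepsy by a local health authority".
- **Section 17.6, Amendment 6, Modifications/Changes**: "Exclusion Criterion 17 and the list of prohibited medications were updated to exclude use of MAOI-A inhibitors and cannabidiols".

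Amendment 7 (Section 17.7) reissued the criterion only to correct its number: "Exclusion Criteria 16 through 20, inclusive, were mistakenly misnumbered". The changes itemised for Amendment 8 (Section 17.8) touch neither Section 4.3.2 nor Section 4.6.

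**The concern.** An entry criterion and a prohibited-medication list should agree, so that nobody enters already taking something the study forbids. Here they agree on two classes and part on the third. A site that screens strictly against Section 4.3.2 finds nothing in Criterion 17 to keep out a child on a non-approved cannabidiol product, yet Section 4.6 forbids the product once the child is in the study.

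The statistical stake lies in Baseline. For direct enrollers the seizure Baseline is the count reported for the 4 weeks before the Screening Visit (Sections 5.1 and 6.1), and percent change and the 50% and 75% responder variables depend on it (Section 4.2.3.2). If the product is stopped at entry, Baseline and treatment differ in two ways: LCM is added and another agent is removed. With no control group the two cannot be separated. Events caused by stopping the product could also count as TEAEs, because any event starting on or after the first LCM dose is treatment-emergent (Section 12.1.2.1.1). If the product is continued, the child is in breach of the protocol from entry.

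**Working it through.** No arithmetic is involved; the check is a comparison of texts.

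**Step 1. Item by item.**

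| Class | Section 4.6 (Amendment 6) | Exclusion 17 (Amendments 6 and 7) |
|---|---|---|
| MAOI-A | prohibited | excluded |
| Narcotic analgesics | prohibited | excluded |
| Cannabidiols not approved or indicated for epilepsy | prohibited | not mentioned |

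Two of the three items match.

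**Step 2. Is either text superseded?** Both are replacement wordings, not the text they replaced. Amendment 6 printed the criterion under number 16 by mistake; Amendment 7 restored number 17 and left the words alone. Nothing itemised in Amendment 8 alters either place.

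**Step 3. Is the difference deliberate?** The Amendment 6 list of changes names the criterion and the prohibited list together and attributes both changes, MAOI-A and cannabidiols, to the pair. That points to an omission. It is supporting evidence only: the conflict between Sections 4.3.2 and 4.6 stands without it.

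**Step 4. Does another criterion close the gap?**

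- Exclusion 1, "Subject is receiving any investigational drugs or using any experimental devices in addition to LCM", catches a cannabidiol taken as an investigational drug, but not a non-approved product obtained in another way.
- Inclusion 4 requires that subject and caregiver "are willing and able to comply with all study requirements, including maintaining a daily seizure diary". Since Section 4.6 is a study requirement, a family that refuses to stop fails it. A family that agrees to stop passes.
- Inclusion 9 asks for stable AED dosing for at least 1 week before Screening. It does not name cannabidiols and sets no condition after Screening.

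**Step 5. Who is left?** A directly enrolling child who takes a non-approved cannabidiol at Screening, outside any investigational use, with a family willing to stop. Nothing shown excludes this child.

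**Step 6. What follows for that child?** The 4 weeks before Screening are counted on the product. If it is then stopped as Section 4.6 requires, the treatment count is made off it. If it is not stopped, Section 4.6 is breached. Section 4.3.3 lists needing a medication that the protocol does not permit among the reasons for which participation may, not must, be discontinued, so the protocol does not settle the outcome.

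**The case against.** The other side has several fair points.

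- **Text seen.** The wording comes from the amendment history; the consolidated Sections 4.3.2 and 4.6 were not in the material reviewed. Amendment 8 mentions typographical corrections, so the body text should be checked first. This stands as a caveat.
- **The list of changes.** Its sentence covers two places at once and could be a loose summary, with cannabidiols meant only for Section 4.6. That is possible, and it is why the point rests on Section 4.6 against Criterion 17.
- **Eligibility.** A reader might infer that every child on such a product is eligible. That is too strong: Inclusion 4 and Exclusion 1 remove some, and concomitant medications are reviewed at Screening, up to 14 days before the first LCM dose. The gap is narrower but not closed.
- **Withdrawal.** A reader might infer that these children would have to leave the study. Section 4.3.3 only allows it.
- **Harm.** Seizure outcomes are secondary and summarised descriptively, there is no primary efficacy variable, and investigators may change, stop or add concomitant AEDs throughout (Section 4.1.1). Change from Baseline therefore already mixes LCM with other treatment changes. This stands and limits the weight of the point. What differs here is that the change would be required by the protocol at entry, in children the entry criterion could have been expected to keep out.

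**Conclusion.** The inconsistency is real in the latest text shown and should be corrected. Its reach is limited to direct enrollers who enter after Amendment 6, take a non-approved cannabidiol at Screening, and are not stopped by Inclusion 4 or Exclusion 1.

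The number cannot be stated. A reader might add up the described direct enrollers, 100 + 46 (Japan) + 60 (China) = 206, and apply an assumed share of users. The documents do not support that. Direct enrollment opened under Amendment 4 and local Amendments 5.2 and 5.4, all numbered before Amendment 6, and the protocol does not say how many children entered later. It is also unclear whether the 46 lie within the 100; if they do, the sum is 160. The protocol gives no figure for cannabidiol use.

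Nor do the documents support a claim that the efficacy or safety conclusions are compromised. They support a conflict between two rules that leaves Baseline and treatment not comparable, or a breach from entry, for an unknown and probably small number of children. This rests on the consolidated sections reading as the amendment history does.

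**What to change.** Reconcile Exclusion Criterion 17 with Section 4.6 and with the change that Amendment 6 says was made, so that the entry criterion and the prohibited list match. Which clinical rule applies, whether it carries a look-back period before Screening, and whether it extends to children entering from EP0060 (for whom Criterion 17 does not apply) are decisions for the sponsor; none of these is settled by the text shown.

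For children already enrolled, use the concomitant-medication records collected from Screening onward to flag non-approved cannabidiol use at Screening, and report how many are flagged when seizure and TEAE data are summarised.

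The cost is one phrase in one section and one flag from data already recorded, plus possibly a few more screen failures, depending on the rule chosen.
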